4.9. Treatment After the End of Study

After the end of the study, each subject will receive treatment according to standard clinical practice.

5. STUDY DRUG MATERIALS AND MANAGEMENT

5.1. Labeling and Packaging

The original labels for the investigational product will contain all information according to regulatory requirements.

5.1.1. Labeling

Fentanyl Sublingual Spray will be supplied as individual subject kits by the sponsor or the sponsor's representative to the investigational sites. Each clinical kit will be labeled with a subject and product label. The investigator or designee will need to record the kit number and subject identification number on the appropriate accountability logs.

5.1.2. Packaging

Fentanyl Sublingual Spray will be supplied by the sponsor or the sponsor's representative. The investigational product is supplied in a unit dose sublingual spray unit packaged in a vial.

5.2. Dispensing and Storage

Fentanyl Sublingual Spray should be stored at 20° to 25°C (68° to 77°F), with excursions permitted between 15° and 30°C (59° to 86°F) until ready to use. Temperature logs should be kept for the storage area.

All investigational products should be stored in a secure location or in the site pharmacy with limited access. It is the responsibility of the investigator to ensure that the investigational product is only used for subjects enrolled in the study.

The investigational product is intended for single use only.

5.3. Drug Supply and Accountability

The investigator must maintain adequate records showing the receipt, dispensing, return, or other disposition of the IP including the date, quantity, and identification of subjects (subject number and initials) who received the IP. If any of the IP is received in a damaged container, this information must be documented and reported to the sponsor, or sponsor's representative.

All unused investigational kits will be returned to the sponsor, or sponsor's representative, when instructed.

6. STUDY ASSESSMENTS

6.1. Efficacy Assessments

6.1.1. Pain Intensity

Subjects will assess their current pain intensity using an 11-point (0 to 10) Numerical Rating Scale (NRS). Each subject will be instructed to mark the number indicating his or her current pain intensity.

The subject is to record pain intensity (NRS) in the inpatient subject diary at Baseline before the first dose of study drug (Day 1), at Time 0. Thereafter, the subject is to record NRS pain intensity assessments at the following time points during the 48-hour period after Time 0:

- 2.5, 5, 15, 30, and 45 minutes and 1, 1.5, 2, 3, 4, 5, 6, 7, 8, 12, 16, 20, 24, 32, 40 and 48 hours after Time 0, and immediately before each use of rescue analgesia.
- At Early Withdrawal if a subject discontinues prematurely.

6.1.2. Pain Relief

Subjects will assess their current pain relief using a 5-point categorical scale. Each subject will be instructed to mark the number indicating his or her current pain relief.

The subject is to record pain relief (5-point categorical rating scale) in the inpatient subject diary at the following time points during the 48-hour period after Time 0:

- 2.5, 5, 15, 30, and 45 minutes and 1, 1.5, 2, 3, 4, 5, 6, 7, 8, 12, 16, 20, 24, 32, 40 and 48 hours after Time 0, and immediately before each use of rescue analgesia.
- At Early Withdrawal if a subject discontinues prematurely.

6.1.3. Two-Stopwatch Assessment of Pain Relief

Time to perceptible pain relief and meaningful pain relief will be evaluated using the 2 stopwatch method (after the first dose only). The study staff will start 2 stopwatches as soon as the first dose of study drug is administered. Each subject will be instructed to stop the first stopwatch when he or she experiences any perceptible pain relief and the second stopwatch when he or she experiences pain relief that is meaningful to them. Subjects will receive training for this procedure at their screening visit and prior to discontinuation of the regional anesthetic popliteal block.

6.1.4. Subject's Global Evaluation of Study Drug

Subjects will complete a subject's global evaluation of study drug at the end of the treatment period (Day 3) before discharge from the study site or immediately before Early Withdrawal if a subject discontinues prematurely. The subject will be instructed to score his or her global evaluation of the study treatment on a 5-point categorical scale where 0 = poor, 1 = fair, 2 = good, 3 = very good, and 4 = excellent.

6.2. Safety Assessments

Safety assessments include the evaluation of AEs, physical and oral examinations, vital sign measurements, pulse oximetry, and 12-lead ECGs. Clinical laboratory tests will be performed at Screening only.

6.2.1. Demographics and Medical History

Each potential study participant will have the following assessments by the Investigator or designee during the Screening Period, within 28 days prior to study start: demographic data, including sex, age, race, ethnicity, body weight (kg), height (cm), and body mass index (BMI [kg/m²]), medical history, medications history, and concomitant medications.

6.2.2. Physical and Oral Examinations

A complete physical examination (excluding the genitourinary examination) will be performed at Screening. An abbreviated physical examination will be performed at the Follow up Visit.

An oral cavity examination will be performed at Screening, on Day 1 prior to and one hour after first dose, and at the Follow up Visit. The oral examination at Screening and prior to first dose will exclude subjects with any active infection, mucositis, cold sores, viral lesions, local irritation, or periodontal disease of the oral cavity. In addition, subjects with recent (within 1 year) piercing of the tongue or anywhere in the oral cavity will be excluded. If there is a recent history of significant dental disease, the investigator may decide to exclude the subject. The oral examinations on Day 1 one hour after first dose and at the Follow up Visit will check for mucositis and local irritation.

6.2.3. Vital Signs

Vital signs, including blood pressure, heart rate, respiratory rate, and oral body temperature, will be measured after the subject has been in a resting position for 5 minutes. Vital signs will be measured at Screening and before surgery on Day 0. From Day 1 through discharge from the study site, vital signs will be measured immediately before and 1 hour after the first dose of study drug on Day 0, then immediately before and 1 hour after the 24 hour and 40 hour doses, and at 48 hours. Vital signs will also be measured before Early Withdrawal if a subject discontinues.

Height, weight, and BMI will be recorded at Screening.

Pulse oximetry will be measured at Screening and continuously after the procedure for safety, and recorded at the following times: baseline before Time 0, and at 90 minutes and 12, 24, and 48 hours after Time 0 (T_{max}).

6.2.4. Electrocardiograms

A standard 12-lead ECG will be performed after the subject has been supine for at least 3 minutes. All ECG recordings will be identified with the subject number, initials, date, and time of the recording. The ECG will be evaluated for any clinically relevant cardiovascular conditions, defined as any clinically significant abnormalities identified by the reader related to coronary artery disease, coronary spasm, abnormal heart rhythm, hypertrophic cardiomyopathy,

heart failure, rheumatic heart disease, or myocarditis. An ECG will be performed after surgery but before the first dose of study drug, and then at 90 minutes and 12, 24, and 48 hours after Time 0.

6.2.5. Clinical Laboratory Assessments

Clinical laboratory tests will be performed at Screening. Pregnancy tests and urine drug screens will be performed at Screening and before surgery. An alcohol breathalyzer test will be performed before surgery. Samples for the following laboratory tests will be collected:

Hematology	hemoglobin, hematocrit, red blood cell count, red blood cell indices, mean corpuscular hemoglobin, mean corpuscular hemoglobin concentration, platelet count (or estimate), and white blood cell count including differential
Serum Chemistry	albumin, total bilirubin, total protein, calcium, alkaline phosphatase, alanine aminotransferase, aspartate aminotransferase, blood urea nitrogen, cholesterol, glucose, sodium, potassium, chloride, bicarbonate, lactate dehydrogenase, uric acid, creatinine with calculated creatinine clearance (Cockcroft-Gault method)
Urinalysis	pH, specific gravity, blood, glucose, protein, ketones
Urine & Serum Pregnancy tests	for women of childbearing potential only; a serum test at Screening and a urine test before surgery
Urine Drug Screen	amphetamines, barbiturates, benzodiazepines, cocaine, opiates, phencyclidine, and tetrahydrocannabinol
Alcohol Breathalyzer	alcohol

Blood and urine samples for hematology, serum chemistry, serum pregnancy test, and urinalysis will be sent to a local laboratory for analyses. Urine drug screens and urine pregnancy tests will be conducted at the study sites.

6.2.6. Adverse Events and Serious Adverse Events

Adverse events will be collected from the time the subject signs an informed consent through the Follow-up visit.

6.2.6.1. Definition of Adverse Events

An AE is defined as any untoward medical occurrence in a subject administered a pharmaceutical product during the course of a clinical investigation. An AE can therefore be any unfavorable and unintended sign, symptom, or disease temporally associated with the use of an investigational product, whether or not thought to be related to the investigational product.

Subjects will be monitored throughout the study for AEs. Monitoring for treatment-emergent AEs will begin as soon as the subject is dosed. All AEs must be followed until they are resolved or stabilized, or until all attempts to determine resolution of the event are exhausted. The investigator should use their discretion in ordering additional tests as necessary to monitor the progress of such events.

An AE may be:

- A new illness, not documented in the subject's medical history;
- Worsening of a concomitant illness;
- An effect of the study medication; it could be an abnormal laboratory value, as well as a significant shift from baseline within normal range which the qualified investigator or medical qualified designate considers to be clinically important;
- A combination of two or more of these factors.

Surgical procedures themselves are not AEs. They are therapeutic measures for conditions that required surgery. The condition for which the surgery is required is an AE, if it occurs or is detected during the study period. Planned surgical measures permitted by the clinical study protocol and the condition(s) leading to these measures are not AEs, if the condition(s) was (were) known before the start of study treatment. In the latter case, the condition should be reported as medical history.

Subjects will be monitored throughout the study for AEs. All AEs must be followed until they are resolved or stabilized, or until all attempts to determine resolution of the event are exhausted. The investigator should use his/her discretion in ordering additional tests as necessary to monitor the progress of such events.

Adverse events reported prior to dose administration will be recorded as part of the subject's medical history.

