6.2.6.3. Classification of Adverse Events

Adverse events are to be recorded on the AE page of the subject's case report form (CRF). Severity will be graded according to the following definitions:

- **Mild:** The subject experiences awareness of symptoms but these are easily tolerated or managed without specific treatment.
- **Moderate:** The subject experiences discomfort enough to cause interference with usual activity, and/or the condition requires specific treatment.
- **Severe:** The subject is incapacitated with inability to work or do usual activity, and/or the event requires significant treatment measures.

Action taken will be categorized as none, study drug discontinued, dose modified, required concomitant medication, required procedure, or other.

Event outcome at resolution or time of last follow-up will be recorded as event resolved, resolved with sequelae, ongoing, or death.

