6.2.6.7. Definition of Serious Adverse Events

A serious AE (SAE) is any AE that fulfills any of the following criteria, as per 21 CFR 312.32:

- Results in death;
- Is life-threatening;
- Requires in-patient hospitalization or prolongation of existing hospitalization;
- Results in persistent or significant disability or incapacity;
- Is a congenital anomaly or birth defect;

- Is medically significant or requires intervention to prevent one of the outcomes listed above.

Serious AEs will be captured from the time of consent through the end of the study

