6.2.6.8. Adverse Event Recording and Reporting

Adverse events will be recorded throughout the study in the source documents and in the CRFs.

If known, the diagnosis should be recorded, in preference to the listing of individual signs and symptoms. Adverse event reporting for each subject starts when the subject signs the informed consent and continues at all subsequent visits through the Follow up Visit. Any preexisting conditions that are detected as part of the screening procedures will need to be reported in the medical history and not as an AE.

The investigator will rate AEs for seriousness, intensity, causality, action taken, and outcome as described in the previous sections.

Expedited reporting is required for serious unexpected adverse drug reactions. Fatal or life-threatening unexpected drug reactions must be reported by the Sponsor to regulatory agencies no more than 7 days after the Sponsor's first knowledge of the reaction; followed by as complete a report as possible within 8 additional days. Unexpected drug reactions must be reported no later than 15 days after the Sponsor's first knowledge of the reaction. In order to comply with these requirements, the investigator or delegate must inform the Sponsor immediately upon occurrence of any SAE. The site will complete the SAE Report Form as thoroughly as possible and fax it to Insys within 24 hours of the investigators first knowledge of the event.

Sponsor contact information is listed below:

[REDACTED]
[REDACTED]
Insys Development Company, Inc.

Email: [REDACTED]

Telephone: [REDACTED]

These SAE reports must contain the following information:

- A. Study name/number
- B. Study drug
- C. Investigator details (name, phone, fax, e-mail)
- D. Subject number
- E. Subject initials
- F. Subject demographics
- G. Clinical event
 - 1) Description
 - 2) Date of onset

- 3) Treatment (drug, dose, dosage form)
 - 4) Adverse event relationship to study drug
 - 5) Action taken regarding study drug in direct relationship to the AE
- H. If the AE was fatal or life-threatening
- I. Cause of death (whether or not the death was related to study drug)
- J. Autopsy findings (if available)

The Sponsor or its representative will be responsible for notification to regulatory agencies.

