7.5. Interim Visits

Subjects should contact the study site if they experience any problems prior to the Follow-up Visit, and an interim visit will be arranged promptly as needed.

Table 2: Schedule of Assessments

	Screening (Days -28 to -1 before surgery)	Surgery Day 0	Treatment Period			Follow-up Day 7 ± 2 days (5 to 9 days after surgery) or Early Withdrawal
			Day 1 (Baseline; before dosing)	Day 1 First dose (Time 0)	Days 2 and 3 Subsequent doses	
Written informed consent	X					
Inclusion/exclusion criteria	X	X				
Demographics	X					
Medical history	X	X ^a				
Physical examination ^b	X					X
Oral examination ^c	X			X		X
Vital signs ^d	X	X	X	X	X	X
Height, weight, and body mass index	X					
Pulse oximetry ^e	X		X	X	X	
12-lead electrocardiogram ^f	X		X	X	X	
Clinical laboratory tests (hematology, chemistry, urinalysis)	X					
Pregnancy test for female subjects ^g	X	X				
Urine drug screen ^h	X	X				
Alcohol breathalyzer test		X				
X-ray and podiatric examination ⁱ	X					
First metatarsal bunionectomy procedure		X				
Discontinue anesthetic block at approximately 3:00 AM ^j			X			
Assign randomization number			X			
Pain assessments ^k			X	X	X	X
Administer study drug ^l				X	X	X

	Screening (Days -28 to -1 before surgery)	Surgery Day 0	Treatment Period			Follow-up Day 7 ± 2 days (5 to 9 days after surgery) or Early Withdrawal
			Day 1 (Baseline; before dosing)	Day 1 First dose (Time 0)	Days 2 and 3 Subsequent doses	
Start stopwatches for perceptible and meaningful pain relief ^m			X			
Subject's global evaluation of study drug ⁿ					X	
Concomitant medications	X	X	X	X	X	X
Adverse events		X	X	X	X	X
Dispense outpatient pain medication and outpatient subject diary ^o					X	
Discharge subject from the study site ^p					X	
Collect and review diary for completion						X

Abbreviations: ET=early termination; NRS=numeric rating scale

a Medical history should be reviewed for any changes since Screening.

b A complete physical examination (excluding the genitourinary examination) will be performed at Screening. An abbreviated physical examination, including an examination of the subject's surgical site, will be performed at the Follow-up Visit.

c The postdose oral examination should be conducted 1 hour (±10 minutes) after dosing.

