7.3.2 Handling of Missing Data For Safety Evaluations

Adverse Event (AE) Summaries

With respect to summaries of AEs, only AEs that were treatment emergent will be tabulated. Treatment-emergent is defined as AEs with start date \geq date of first treatment administration.

- 1) If AE start date is completely missing, the date of first treatment administration will be taken as the start date of the event.
- 2) If AE start date is partially missing:
 - a. If the day part of the start date is missing, the start date will be estimated to be equal to the date of first treatment administration, provided the start month and year are the same as the date of first treatment administration and the stop date either after the

date of first treatment administration or completely missing. Otherwise, the AE will be assumed to have started on the first day of the month (01/MMM/YYYY)

- b. If the month part of the start date is missing, the start month will be estimated to be equal to the month of the date of first treatment administration or the following month after the month of the date of first treatment administration depending on the day part of the start date provided that the start year is the same as the year of date of first treatment administration and the stop date is either after date of first treatment administration or completely missing. Otherwise, the AE will be assumed to have started on the first month of the year (DD/Jan/YYYY)
- c. If both the day and month parts of the start date are missing, the start date will be estimated to be equal to the date of first treatment administration, provided the start year is the same as year of date of first treatment administration and the stop date is either after the date of first treatment administration or completely missing. Otherwise, the AE will be assumed to have started on first day and first month of the year (01/Jan/YYYY)
- d. If all day, month and year parts of the start date are missing, the start date will be estimated to be equal to the date of first treatment administration (and thus treatment emergent) provided that the stop date is either after the date of first treatment administration or completely missing. Otherwise, the start date will be estimated to be the first day of the same year as the stop date.

3) If AE stop date is partially or completely missing:

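### The protocol gives conflicting rules for recording pre-dose adverse events, and because the SAP defines treatment-emergence by start date alone, whether such events are counted depends on the rule a site follows

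*Protocol*

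**What the plan says.** On where a pre-dose event is recorded, the protocol gives two rules.

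- **Medical history.** Section 6.2.6.1 has a sentence beginning "Adverse events reported prior to dose administration will be recorded as part of the" and ending with the subject's medical history. It covers any event reported before dosing, with no limit to conditions that predate consent.
- **AE from consent.** Section 6.2.6 states: "Adverse events will be collected from the time the subject signs an informed consent through the Follow-up visit". Section 6.2.6.8 agrees: "Adverse event reporting for each subject starts when the subject signs the informed consent". For serious events, 6.2.6.7 says: "Serious AEs will be captured from the time of consent through the end of the study". Section 6.2.6.3 names the place: "Adverse events are to be recorded on the AE page of the" case report form (CRF). Section 7.2.1 item 7 records AEs before surgery, and the AE row of Table 2 is marked on Day 0 and on Day 1 before dosing.

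Section 6.2.6.8 also has a narrower medical-history rule: "Any preexisting conditions that are detected as part of the screening procedures will need to be reported in the medical history". That one is compatible with collecting AEs from consent.

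On what is counted, SAP 7.3.2 tabulates treatment-emergent events (TEAEs) only: "Treatment-emergent is defined as AEs with start date" on or after the date of first treatment. SAP 8.2.4 uses the same date window, and Protocol 8.5.4.1 limits AE summaries to TEAEs. Neither SAP section mentions time of day or worsening.

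**The concern.** Every subject has surgery on Day 0 and can be dosed only on Day 1, so there is always an interval in which symptoms may arise before study drug. Hydrocodone/acetaminophen is permitted in that interval (Protocol 4.8 and 7.2.2), and Appendix 5 provides for postoperative nausea and emesis. Nausea, vomiting and somnolence are also among the fentanyl effects named in Protocol 1.5. The events most likely to fall in the disputed interval are thus of the same kind as the drug effects the safety tables are meant to show.

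Safety against placebo is a secondary objective (Protocol 2.2). If sites record the same symptom differently, the TEAE tables reflect recording habit as well as treatment. With about 15 subjects per arm, one or two such cases are visible in a percentage.

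**Working it through.** The documents state no figure on this point, so there is none to reproduce. The check applies each recording rule, together with the SAP date rule, to nausea that begins before the first dose.

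**Inputs**

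1. Surgery is on Day 0. The block is stopped at about 3:00 AM on Day 1, and the first dose follows within 9 hours (Protocol 7.3.1, 7.3.2).
2. Protocol 6.2.6.1 lists the worsening of an existing illness as an AE in its own right.
3. An event is treatment-emergent if its start date is on or after the date of first dose (SAP 7.3.2, 8.2.4).
4. No general rule requires an increase in severity to be entered as a new AE record. Protocol 8.5.4.5 has such a rule only for physical and oral examination findings.

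**Is the event in the TEAE tables?**

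| Onset | After dosing | Recorded as medical history | Recorded as an AE from consent |
|---|---|---|---|
| Day 0 | does not worsen | no | no |
| Day 0 | worsens | yes, if the worsening is entered as an AE | no, if kept as one record; yes, if the worsening is a new record |
| Day 1, pre-dose | does not worsen | no | yes, because start date equals dose date |
| Day 1, pre-dose | worsens | yes, if the worsening is entered as an AE | yes |

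The rules diverge in row 2, where the AE record can lose the event, and in row 3, where the AE record adds an event that cannot be due to study drug. Row 3 also sits badly with Protocol 6.2.6.1, which starts monitoring for TEAEs at dosing.

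The instruction in SAP 8.2.4 to summarise the worst severity does not rescue row 2. It selects among records already in the window, and this record is outside it.

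**Which rule will a site follow?** Medical history is scheduled at Screening and once more before surgery on Day 0 (Protocol 7.2.1 item 1; Table 2, footnote a: "Medical history should be reviewed for any changes since Screening"). No review is scheduled between surgery and first dose, while the AE row is open then. The schedule therefore favours the AE record, but 6.2.6.1 tells the site otherwise.

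**Size.** Assume all 15 planned subjects per arm are treated. For a given event term, one reclassified subject moves that arm's incidence by 1/15 = 6.7 percentage points. An overall any-TEAE rate moves only if the subject has no other TEAE.

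For the difference between a fentanyl arm and placebo, let a and b be the subjects lost through row 2 on fentanyl and placebo, and c and d those added through row 3. Recording as one AE record rather than as medical history changes the difference by

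[(c − d) − (a − b)] / 15.

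None of a, b, c or d is given in the documents. Assuming a net imbalance of −2 to +2 subjects, the change runs from −2/15 = −13.3 points to +2/15 = +13.3 points.

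**The case against.** The strongest reply is that the documents never require the loss. The clause in 6.2.6.1 that makes a worsening an AE can be applied to an ongoing AE as readily as to a medical-history item. Read that way, the worsening is a post-dose AE under either rule. This stands in part: the row 2 loss is conditional on the site keeping one continuing record. But neither document says to open a new record, so the outcome is left to site practice.

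A reader might go further and infer that worsening nausea is necessarily lost under one rule, or that the safety comparison is biased toward no difference. The documents support neither. The first ignores re-recording. The second looks only at Day 0 onset, whereas Day 1 pre-dose onset adds events instead of removing them.

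Other points limit the effect:

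- Exclusion criterion 25 removes subjects with a history or presence of postoperative vomiting of grade 2 or higher, and criterion 2 allows exclusion for surgical complications. Nausea, dizziness and milder vomiting remain.
- Safety is descriptive, with no inferential testing (Protocol 8.5.4, SAP 8.2.3).
- All collected data are listed (SAP 8), and concomitant medications and reasons for discontinuation are summarised by arm. A missed worsening could be traced, though it would still be missing from the TEAE tables.
- Section 7.2.1 item 7 is a pre-surgery step. It shows that AEs are recorded before dosing but does not itself address post-surgical symptoms.

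**Conclusion.** The concern holds in a conditional form. Protocol 6.2.6.1 contradicts 6.2.6, 6.2.6.7, 6.2.6.8 and Table 2 on where pre-dose events go, and the SAP's date-only definition turns that contradiction into different TEAE counts. The result depends on the recording rule, the day of onset, and whether a worsening is entered as a new record.

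The only size that rests on the documents is 6.7 points per reclassified subject, assuming 15 treated subjects per arm. The number of such subjects, their split between arms and the direction of any net bias are unknown. The primary efficacy analysis is not affected. The point still merits a correction, because a stated rule can miscount safety events, which is more than a missing detail.

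**What to change.** 1. **Protocol 6.2.6.1.** Limit the medical-history sentence to conditions present before consent, and record events arising between consent and first dose as AEs. This brings it into line with 6.2.6, 6.2.6.7, 6.2.6.8 and Table 2.
2. **SAP 7.3.2 and 8.2.4.** Define treatment-emergent in both as an AE that starts, or increases in severity, after the date and time of first dose. Changing only one section would leave the SAP contradicting itself.
3. **Recording rule.** Require an increase in severity after first dose to be entered as a new AE record with its own onset date and time. State how a Day 1 event with no onset time is classified.

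The cost is one protocol sentence, matching wording in two SAP sections, a CRF completion note, collection of AE onset times, and slightly more AE records. Design and sample size do not change.
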